11.2.1 Study Endpoints

This sub-study includes the assessment of one primary effectiveness endpoint, as well as three secondary endpoints. The hypothesis associated with the primary endpoint is in a superiority format.

* Subjects may be enrolled in the MPP sub-study at the 3-Month QP ExCELS follow-up if the subject received continuous standard biventricular (BiV) pacing from implant to the 3-Month follow-up with a HF hospitalization event and will be followed for 6 months in the MPP sub-study with MPP sub-study data collected at a 6-month follow-up and 9-month follow-up.

11.2.1.1 Primary Endpoint 1

The purpose of primary endpoint 1 is to evaluate the CRT responder status with the MPP feature within the Ilivia 7 HF-T QP family CRT-D, or future-marketed CRT-D system, compared to a pre-specified performance goal.

The associated hypothesis is evaluated based on a CCS determining a responder classification based on changes in NYHA class, HF hospitalization, and cardiovascular death.

A responder status will be derived classifying these subjects as “Improved”, “Worsened”, or “Unchanged” using the following definitions:

Responder Classification at 12-Month Follow-up (evaluated compared to MPP Enrollment Visit occurring at 6 months)[†]:

- “Improved”:
 - No HF hospitalization or cardiovascular death, AND
 - NYHA class is improved
- “Unchanged”:
 - No HF hospitalization or cardiovascular death, AND
 - NYHA class is unchanged
- “Worsened”:
 - HF hospitalization or cardiovascular death has occurred, OR
 - NYHA class is worsened

Ho: The proportion of subjects (P) who are classified as “Improved” is not superior to a performance goal (PG) of 3%.

$$PG \geq P$$

Ha: The proportion of subjects who are classified as “Improved” is superior to a performance goal of 3%.

$$PG < P$$

A rejection of the null hypothesis would indicate that the proportion of subjects classified as “Improved” is superior to 3%.

11.2.1.2 Secondary Endpoint 1- Freedom from MPP system related adverse events requiring additional invasive intervention to resolve at 6 months

The purpose of Secondary Endpoint 1 is to evaluate adverse events that require additional invasive intervention to resolve, specifically related to the MPP feature of the Ilivia HF-T QP family, or future-marketed CRT-D system with the MPP feature. These adverse events include any software issues related to MPP programming or any adverse event that occurs while MPP is enabled and that may be attributed to the use of the MPP feature.

[†] Evaluated at 9-month follow-up if MPP sub-study enrollment visit occurred at 3 months.

11.2.1.3 Secondary Endpoint 2 - Evaluate CCS + PGA Responder Status utilizing a modified CCS that incorporates the Patient Global Assessment

The purpose of Secondary Endpoint 2 is to evaluate a modified CCS, determining a responder classification based on changes in NYHA class, Patient Global Assessment (PGA), HF hospitalization, and cardiovascular death, where the PGA will ask subjects to assess how their overall status has changed since prior to receiving CRT therapy (markedly better, better, unchanged, worse, markedly worse).

Modified Responder Classification (CCS + PGA) at 12-Month Follow-up[‡]:

- “Improved”:
 - No HF hospitalization or cardiovascular death, AND
 - Neither NYHA class is worsened or PGA is worsened (“worse” or “markedly worse”), AND
 - NYHA class is improved or PGA is improved (“better” or “markedly better”)
- “Unchanged”:
 - No HF hospitalization or cardiovascular death, AND
 - NYHA class is unchanged, AND
 - PGA is unchanged (“unchanged”)
- “Worsened”:
 - HF hospitalization or cardiovascular death has occurred, OR
 - NYHA class is worsened or PGA is worsened (“worse” or “markedly worse”)

11.2.1.4 Secondary Endpoint 3: Evaluate CCS Responder Status utilizing a modified Responder Classification

The purpose of Secondary Endpoint 3 is to evaluate a modified Responder Classification in which both “Improved” and “Unchanged” subjects will be classified as responders. At the time of enrollment into the MPP sub-study, MPP sub-study subjects have already been found to have no change or worsening in their HF status with BiV pacing. Since HF is a chronic and progressive condition, these subjects may be expected to continue to worsen during the MPP follow-up period or remain stable with careful management. In this secondary endpoint, a status of “Unchanged” (in addition to “Improved”) during the MPP follow-up period will be considered a responder to MPP.

[‡] Evaluated at 9-month follow-up if MPP sub-study enrollment visit occurred at 3 months.

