11.2 Sub-Study Design

The objective of this MultiPole Pacing sub-study is to demonstrate that the MPP feature is effective by converting a percentage of CRT non-responders to responders. Each subject's responder status will be assessed using a Clinical Composite Score (CCS)⁴ including three components: NYHA Class, heart failure (HF) hospitalizations, and cardiovascular death.

The MPP sub-study is a single-arm, multi-center, prospective trial within the ongoing QP ExCELS study. Eligible patients will have been enrolled in QP ExCELS and successfully implanted with the BIOTRONIK Ilivia HF-T QP family CRT-D system, or future-marketed CRT-D system with the MPP feature, and have received standard biventricular (BiV) pacing (i.e. without MPP) prior to a 6-Month CCS assessment or at the time of the QP ExCELS 3-month follow-up with a HF hospitalization event.

Visit intervals below are specified according to time since implant to minimize confusion between the differing enrollment timing into the QP ExCELS study and MPP sub-study.

At the QP ExCELS 6-month Follow-up, a CCS assessment will be completed for all QP ExCELS enrolled subjects who are currently receiving BiV pacing, including NYHA class and HF hospitalization status. Additionally, a Patient Global Assessment (PGA) will be collected. A responder status will be derived classifying these subjects as "Improved", "Worsened", or "Unchanged" using the following definitions:

CRT Responder Classification at QP ExCELS 6-Month Follow-up (evaluated compared to QP ExCELS Enrollment Visit)*:

- “Improved”:
 - No HF hospitalization has occurred, AND
 - NYHA class is improved
- “Unchanged”:
 - No HF hospitalization has occurred, AND
 - NYHA class is unchanged
- “Worsened”:
 - HF hospitalization has occurred, OR
 - NYHA class is worsened

Classification of prior “HF hospitalization” event at the time of MPP screening/enrollment and NYHA class will be determined and reported by the investigator.

Those subjects responder classification determined to be “Worsened” or “Unchanged” may be approached for enrollment into the MPP sub-study. These subjects must sign a separate MPP sub-study Informed Consent prior to enrollment. Those that decline enrolling into the MPP sub-study will continue to be followed according to the primary QP ExCELS protocol.

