11.2.1.5 Additional Data of Interest

Additional information will be collected to characterize the study population, implanted system, and progress of the clinical investigation. The data will be statistically analyzed, where appropriate. Further data of interest will include:

- Patient Global Assessment (PGA) at each visit
- MPP programmed settings
- Adverse events attributed to MPP feature
- Device initial and final programmed settings
- Methods utilized to optimize MPP, AV and/or V-V timing

11.2.2 **Study Size and Duration**

The MPP sub-study will enroll up to 100 subjects at up to 75 sites within the United States who are participating in the QP ExCELS study. Subjects in the MPP sub-study will be followed for 6 months (180 ± 30 days post-MPP enrollment). Subjects enrolled in the MPP sub-study will rejoin the main QP ExCELS study after completion of their 12-month MPP follow-up[§].

11.2.3 **Sample-Size Analysis**

The investigation is designed to limit the number of patients involved while still exposing the device to a sufficiently large patient population in order to ensure a representative and statistically meaningful sample.

Primary Endpoint 1 Sample Size

The estimated sample size requirements are based on a superiority comparison of the proportion of responders to a performance goal of 3%, chosen based on the assumption that any conversion of non-responders to responders is clinically relevant. A performance goal of 3% was chosen rather than 0% to account for variability (“noise”) around 0%, for example, due to infrequent subjects who are late responders to CRT or improve regardless of MPP. The expected result is estimated at a 10% conversion of non-responders to responders.

There is limited published data available for mid- to long-term follow-up CRT response with multiple point LV pacing in any population. Additionally, no published data could be found related to CRT response with multiple point LV pacing in an “all-comer non-responder” population. The St. Jude Medical MultiPoint Pacing IDE Study^{3,5} (“St. Jude IDE study”, NCT01786993) evaluated CRT response based on a Clinical Composite Score (CCS) after 3 months of BiV pacing. Subjects were then randomized to the MultiPoint™ Pacing treatment arm

[§] If an MPP sub-study subject was enrolled at the 3-Month QP ExCELS follow-up, they will re-join the main QP ExCELS study after completion of their 9-month MPP follow-up.

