11.2.4 Data Analyses

Classification of "HF hospitalization" and "cardiovascular death" events for use in primary endpoint 1, secondary endpoint 2, and secondary endpoint 3 analyses will be determined by a Clinical Events Committee (Section 11.3.4).

Descriptive statistics will be used to present and summarize the data collected in the clinical study. Frequency distributions and cross tabulations will be presented for discrete variables. Means, standard errors, and ranges will be presented for continuous variables.

For primary endpoint 1, the lower, one-sided, exact 97.5% bound for the observed proportion of responders ("improved") would have to exceed 3% for rejection of the null hypothesis.

Additional related analyses to be performed for the endpoint include:

- Descriptive statistics for observed changes in NYHA class and frequency tabulations for the other components of the Clinical Composite Score.

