11.3.2.2 Patient Global Assessment (PGA)

[figure not shown]
During the course of the study a patient global assessment will be given to assess how the subject's overall status has changed since prior to receiving CRT therapy (markedly better, better, unchanged, worse, markedly worse). It is important to minimize the influence on the respondent by limiting their interaction and verbal exchanges with spouses or other individuals who may affect results while the assessment form is being completed.

** Subjects enrolled in the MPP sub-study at the 3-Month QP ExCELS follow-up, qualifying with a HF hospitalization event, will rejoin the main QP ExCELS study after the 9-Month Follow-up

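### Does judging improvement from MPP enrolment, when non-response was judged from before CRT, call for a change to the MPP sub-study plan?

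*Combined protocol and SAP*

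**What the plan says.** Section 11.2 states the aim of the sub-study as to "demonstrate that the MPP feature is effective by converting a percentage of CRT non-responders to responders". It fixes the reference for entry: "CRT Responder Classification at QP ExCELS 6-Month Follow-up (evaluated compared to QP ExCELS Enrollment Visit". That visit precedes implantation (Section 3.4.3), so entry status is a comparison with the pre-CRT state. Subjects classed Unchanged or Worsened may enter. Worsened means either a heart failure (HF) hospitalisation or a worse NYHA class.

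Section 11.2.1.1 fixes a different reference for the primary endpoint: "Responder Classification at 12-Month Follow-up (evaluated compared to MPP Enrollment Visit occurring at 6 months". Subjects who enter at 3 months after an HF hospitalisation are assessed at 9 months instead. Improved requires a better NYHA class and no HF hospitalisation or cardiovascular death. The conclusion is worded narrowly: "A rejection of the null hypothesis would indicate that the proportion of subjects classified as" Improved is superior to 3%.

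Three other provisions bear on the point.

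- Secondary Endpoint 2 (Section 11.2.1.3) adds the Patient Global Assessment (PGA) and requires for Improved that "Neither NYHA class is worsened or PGA is worsened". The PGA asks how "overall status has changed since prior to receiving CRT therapy" (Section 11.3.2.2).
- Section 11.2.1.5 lists "Patient Global Assessment (PGA) at each visit" among the additional data.
- Section 11.2.4 plans descriptive statistics of NYHA change and says "Frequency distributions and cross tabulations will be presented for discrete variables". It names neither the visits to be crossed nor a split by entry route.

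**The concern.** The words Improved, Unchanged and Worsened are used at both stages, but the baseline moves between them. A subject who lost a NYHA class on biventricular pacing and regains it on MPP is counted as Improved. On NYHA class, the comparison that made this subject a non-responder would now read unchanged.

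The aim is stated as conversion of non-responders. A reader could take the primary result as the share of subjects now better than before CRT, which it is not. The trial has a single arm and a low bar, so a handful of such subjects could make up much of a passing result. No named output says how many there are.

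**Working it through.** **1. The plan's own figure.** Inputs from Sections 11.2.3, 11.2.4 and 11.2.4.1: performance goal 3%, expected 10%, one-sided alpha 0.025, power 80%, exact lower 97.5% bound above 3%, 10% loss.

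P(X ≥ r | n, p) = Σ(k = r to n) C(n,k) p^k (1 − p)^(n − k)

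- n = 90, r = 7: P(X ≥ 7 | 0.03) = 0.0188, which is below 0.025; power P(X ≥ 7 | 0.10) = 0.8075.
- n = 89, r = 7: power 0.7983, so 90 is the smallest n that reaches 80%.
- Enrolment: 90 / 0.9 = 100.
- The lower bound L solves P(X ≥ x | 90, L) = 0.025: 7/90 gives 3.18% (pass), 6/90 gives 2.49% (fail).

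The stated 90 and 100 are reproduced. None of these figures depends on a pre-CRT comparison.

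**2. Which entrants are affected.** Illustrative NYHA paths, each with no event after MPP enrolment:

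| Entry route | Pre-CRT | MPP enrolment | Final visit | Section 11.2.1.1 | Final class against pre-CRT |
|---|---|---|---|---|---|
| Unchanged | III | III | II | Improved | better |
| Worsened by NYHA only | II | III | II | Improved | same |
| Worsened by HF hospitalisation, NYHA stable | III | III | II | Improved | better |

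Only entrants whose NYHA class had fallen by MPP enrolment can be Improved by regaining the old class.

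**3. Would the pre-CRT reference be better?** The entry rule is a composite. If it were applied unchanged from main-study enrolment to the final visit, everyone who entered through an HF hospitalisation would stay Worsened whatever MPP did, because the hospitalisation has already occurred. The subject in the third row could never be converted. Counting NYHA from before CRT but events from MPP enrolment would avoid that, but neither section contains this hybrid rule. It would also require an entrant who had dropped one class to gain two on MPP, so deterioration under biventricular pacing would count against MPP. Taking both components from MPP enrolment gives every entrant the same starting line.

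**4. What existing outputs show.** Taking NYHA change in Secondary Endpoint 2 from MPP enrolment, as in the primary endpoint, a returner with a worse PGA becomes Worsened. A returner whose PGA is unchanged or better stays Improved. This is a partial check. The full check needs NYHA at three visits: main-study enrolment (Section 3.4.2), MPP enrolment (Section 11.3.3.1) and the final MPP visit (Section 11.3.3.3). All three are collected.

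**5. Possible size.** The documents give neither the number m of entrants with worsened NYHA nor the fraction g who return to their old class. Assume m = 9, 18 or 27 (10%, 20% or 30% of 90) and g = 20% or 30%, with nobody else improving. The expected number of returners is m × g:

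| m | g = 20%: expected | P(7 or more) | g = 30%: expected | P(7 or more) |
|---|---|---|---|---|
| 9 | 1.8 | 0.03% | 2.7 | 0.4% |
| 18 | 3.6 | 5.1% | 5.4 | 27.8% |
| 27 | 5.4 | 28.7% | 8.1 | 74.4% |

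The range runs from negligible to large and rests wholly on assumed inputs.

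**The case for a change.** The strongest case for a change is that Section 11.2.4 permits the relevant table without committing to it. At the minimum passing result of 7 of 90, one subject who only regained the pre-CRT class decides whether the goal would also be met against the pre-CRT visit. Naming a table of NYHA at the three visits by entry route would cost little and would settle in advance what may be said about conversion.

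The observation about the text stands: the references differ, and no such table is named. Such a table would be a reasonable descriptive addition, with events counted from MPP enrolment and no pass/fail role.

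The rest does not carry a change. The pre-CRT count is not the endpoint, so failing it would contradict no stated claim. The probabilities above describe success on an endpoint whose definition is not in dispute, and they do not separate regain caused by MPP from regain that would have happened anyway. Regain without MPP is a question of having no control arm. Section 11.2.3 sets the goal above zero partly for subjects who improve regardless of MPP, and whether 3% is enough for that is separate from the choice of reference visit. Section 11.2.1.4 also expects these patients may keep worsening because heart failure is progressive. On that view, regaining a lost class on MPP is a response.

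**Conclusion.** No change is needed. The two reference visits answer two questions: who failed to respond to biventricular pacing, and who improved after MPP was switched on. The second is the proper subject of the primary endpoint, and its conclusion is worded to match. The success rule (7 of 90), the sample size (90 evaluable, 100 enrolled) and the power (80.75%) are unaffected.

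What remains is a reporting detail: how many Improved subjects ended above their pre-CRT class and how many only returned to it. Its size cannot be fixed from the documents; under the assumed inputs the expected number of returners runs from 1.8 to 8.1. Analysts can give the count from data already collected, under the summaries Section 11.2.4 already provides for. The conclusion assumes that the result is reported as improvement from MPP enrolment, as Section 11.2.1.1 defines it, and not as improvement over the pre-CRT state.

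### MPP secondary endpoint 2 scores a PGA answer anchored to before CRT, so its PGA component cannot separate change under BiV pacing from change under MPP

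*Combined protocol and SAP*

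**What the plan says.** Section 11.2 gives the objective: to "demonstrate that the MPP feature is effective by converting a percentage of CRT non-responders to responders". Subjects enter on a classification built from NYHA class and HF hospitalization, "evaluated compared to QP ExCELS Enrollment Visit". A PGA is collected at that visit but plays no part in the entry classification. Primary endpoint 1 (11.2.1.1) uses the same components plus cardiovascular death and is "evaluated compared to MPP Enrollment Visit occurring at 6 months".

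Secondary endpoint 2 (11.2.1.3) adds the PGA. The "PGA will ask subjects to assess how their overall status has changed since prior to receiving CRT therapy", on five categories from markedly better to markedly worse; section 11.3.2.2 repeats that anchor. The heading gives an assessment visit but no comparison visit: "Modified Responder Classification (CCS + PGA) at 12-Month Follow-up". Its footnote only moves the visit: "Evaluated at 9-month follow-up if MPP sub-study enrollment visit occurred at 3 months". Besides freedom from HF hospitalization and cardiovascular death, *Improved* requires "Neither NYHA class is worsened or PGA is worsened" and also "NYHA class is improved or PGA is improved". The brackets in the rule define PGA improved as an answer of better or markedly better, and PGA worsened as worse or markedly worse.

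The PGA is obtained at MPP enrolment (11.3.3.1, item 5) and at both MPP follow-ups (11.3.3.2 and 11.3.3.3). Section 11.2.1.5 lists it at each visit as data of interest, and 11.2.4 provides in general terms for cross tabulation of discrete variables.

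Two passages point towards a comparison with enrolment. The introduction to 11.2.1.3 describes the classification as resting on change in the PGA, among other components. Section 11.2.4.2 says that a PGA missing at enrolment, as well as at follow-up, affects how many subjects can be analysed. Neither states how the two answers would be compared.

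**The concern.** Every sub-study subject has had months of BiV pacing before MPP is switched on. A final answer about change since before CRT covers the BiV period and the MPP period together. Because the entry classification ignores the PGA, a subject can enter as a non-responder on NYHA and HF hospitalization while already reporting *better*. That subject meets the PGA condition for *Improved* on the day MPP is activated.

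At stake is what the reported *Improved* and *Worsened* rates mean. This is one of three listed secondary endpoints of an FDA-required post-approval study, and its rates will naturally be read as results of MPP. Their PGA part does not measure that.

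**Working it through.** **Reference points side by side**

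| Classification | Components | Compared with |
|---|---|---|
| Entry (11.2) | NYHA, HF hospitalization | QP ExCELS enrolment |
| Primary endpoint 1 (11.2.1.1) | NYHA, HF hospitalization, CV death | MPP enrolment |
| Secondary endpoint 2 (11.2.1.3), NYHA and events | same as primary | not named |
| Secondary endpoint 2, PGA | final answer category | status before CRT, fixed by the question |

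**Two cases, no event during MPP**

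- NYHA unchanged from MPP enrolment, PGA *better* at enrolment and *better* at the final visit: secondary endpoint 2 gives *Improved*, primary endpoint 1 gives *Unchanged*.
- NYHA improved, PGA from *markedly worse* to *worse*: secondary endpoint 2 gives *Worsened*, because the PGA condition overrides the NYHA gain; primary endpoint 1 gives *Improved*.

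**Enumeration**

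Take the five categories MB, B, U, W, MW (markedly better to markedly worse) at enrolment and at the final visit: 5 × 5 = 25 pairs. Assume no event, and NYHA compared with MPP enrolment. Compare the protocol's rule (category of the final answer) with a change rule (direction of movement from the enrolment category).

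| NYHA | Pairs that agree | Protocol rule more favourable | Protocol rule less favourable |
|---|---|---|---|
| Unchanged | 15 | 5 | 5 |
| Improved | 19 | 3 | 3 |
| Worsened | 25 | 0 | 0 |

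Pairs below are written enrolment–final.

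- NYHA unchanged, protocol rule more favourable: MB–MB, MB–B, MB–U, B–B, B–U. Less favourable: W–U, W–W, MW–U, MW–W, MW–MW.
- NYHA improved, protocol rule *Improved* but change rule *Worsened*: MB–B, MB–U, B–U. The reverse: W–W, MW–W, MW–MW.
- With NYHA unchanged, the protocol rule calls 10 pairs *Improved*. Of these, 7 have a better category than at enrolment, 2 the same and 1 a worse one. The 10 pairs called *Worsened* mirror this.
- With an HF hospitalization or cardiovascular death, both rules give *Worsened*.

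These are counts of answer pairs, not of subjects. They show where the two rules part, not how often. The change rule is a comparator, not a known truth: the same answer at two visits does not prove that nothing changed.

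**What does not depend on the PGA**

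The plan gives no sample size or test for secondary endpoint 2. The only sized MPP endpoint is primary endpoint 1, which uses NYHA and events. Its figure reproduces with the exact binomial test: at n = 90 the null of 3% is rejected with 7 or more responders, the one-sided error is 0.0188 and the power at 10% is 0.8075. Enrolment is 90/0.9 = 100. Secondary endpoint 3 reclassifies the primary categories and does not use the PGA either.

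**The case against.** **The text may intend a comparison with enrolment.** The introduction to 11.2.1.3 speaks of change in the PGA. Section 11.2.4.2 treats a missing enrolment PGA as affecting who can be analysed, which would not follow if only the final answer were scored. This stands as a real ambiguity, and the passages should be reconciled. It does not remove the point, because the operative rule attaches improved and worsened to categories of the final answer and no section gives a change rule.

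**The missing reference visit is largely editorial for NYHA.** The endpoint modifies a score defined earlier in 11.2.1 against MPP enrolment, so a reader would probably infer that visit. That is fair. It does not help the PGA, whose reference is built into the question.

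**Entry selects subjects who have not improved.** Entrants are unchanged or worsened on NYHA and HF hospitalization against QP ExCELS enrolment. For an *Unchanged* entrant, NYHA before CRT and at MPP enrolment coincide; for some *Worsened* entrants the pre-CRT anchor may be the stricter one. This limits what can be said about frequency. It does not rule out a PGA of *better* at entry, since the PGA is not used there.

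**The change can be shown without altering the endpoint.** The PGA is collected at each MPP visit and cross tabulations are planned. True, and it makes the remedy cheap. But no enrolment-by-final PGA table is named, and the endpoint rule stays as it is.

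**A change rule is itself a preference.** With improved NYHA, a move from *markedly better* to *better* would be scored *Worsened*, although the subject still reports being better than before CRT. This stands, and it argues for reporting both versions rather than replacing one with the other.

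**Conclusion.** The point holds in a limited form. The PGA component of secondary endpoint 2, as its rule is written, measures change since before CRT and cannot be read as change on MPP. This follows from the scoring brackets in 11.2.1.3, the anchor stated there and in 11.3.2.2, and an entry rule that ignores the PGA.

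A reader might infer that the endpoint is biased in favour of MPP. The documents do not support that. For illustration, let q be the share already *better* or *markedly better* at MPP enrolment and h the share with an event or worsened NYHA, independent of q. With no PGA change and no NYHA improvement on MPP, the *Improved* rate is q(1 − h). For assumed q of 10% to 50% and h of 0 to 30% it runs from 0.10 × 0.70 = 7% to 0.50 × 1.00 = 50%. Both inputs are assumptions, since the documents give no PGA distribution. The rule can also understate gains, as in the move from *markedly worse* to *worse*. The pair counts are symmetric by construction and settle nothing about net direction. Size and direction are unknown.

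A reader might also infer that the sub-study's main result is compromised. It is not: primary endpoint 1, secondary endpoint 3 and the 90 evaluable subjects do not depend on the PGA, and secondary endpoint 2 has no hypothesis or performance goal. The change should be made, but it is not critical to the sub-study.

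**What to change.** In 11.2.1.3:

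1. Name the MPP enrolment visit as the reference for NYHA class and events, as 11.2.1.1 does.
2. State whether the enrolment PGA enters the classification, and reconcile the rule with its own introduction and with 11.2.4.2.
3. Beside the classification as it stands, pre-specify a second version in which the PGA is scored as change in category from MPP enrolment (11.3.3.1, item 5) to the final MPP visit: 12 months, or 9 months for those enrolled at 3 months.
4. Name the enrolment-by-final PGA table among the cross tabulations of 11.2.4.
5. State that the rate under the existing rule measures change since before CRT and is not to be read as change on MPP.

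The cost is a wording change, one additional classification and one table; no new data are needed. The change version has its own limits. A subject at *markedly better* cannot move up and one at *markedly worse* cannot move down. Change within a category is not seen. A subject with improved NYHA who goes from *markedly better* to *better* is scored *Worsened*. These limits are why both versions should be reported.
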